Once the project is completed, both groups will be asked to complete a Common Data Element Survey as requested by the NIH's terms and conditions. A priority of the RADx initiative is to build the RADx Data Hub, the NIH's resources of RADx-generated research data that can help other researchers and public health officials better understand the impact of the COVID-19 pandemic, including outcomes, disparities, and possible solutions. RADx-UP projects collect data for the RADx Data Hub and simplify the analysis of that data, the NIH defined a set of Common Data Elements (CDEs). The NIH RADx-UP CDEs provide a standard set of study questions that RADx-UP projects are required to use in their COVID-19 studies. Additional information can be found at <https://radx-up.org/learning-resources/cdes/>

9. Surveys, questionnaires, or psychological tests: If your study uses surveys, questionnaires, or psychological tests, please list and describe the setting, mode of administration, the length of administration time, number of repeats, and if special training or qualifications are necessary to administer the study instruments. Describe provisions for maintaining privacy and confidentiality.

All the following surveys and questionnaires will be comprehensible to participants by ensuring readability checks on the type of language used, simplicity of language, and additional explanation of concepts.

A basic demographic survey (**see attached: Basic Demographic Survey**) will be administered on a phone call when the patient has been consented and enrolled in the study. In this demographic survey, the survey consists of demographic questions such as age, race and ethnicity, education level, and other sociodemographic questions and will take about 10 minutes to complete.

Pre- and post- surveys (**see attached: Pre- and Post- RADxUP Survey**) will be administered telephonically by study staff to enrolled study participants. These surveys will be provided to both control and case arms, to measure three key measures: trust, self-efficacy,

and intent to participate in COVID-19 testing and vaccination. Secondary measures included will use brief measures from the RADxUP and Phenx database of COVID protocols such as worry about COVID-19, knowledge, attitudes, behaviors, social support, perceived COVID-19 threat, and sources of information about COVID-19.

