CDE Survey - The questions on this survey are required to be collected, as noted in the NIH's terms and conditions of funding the project. The project staff is in the process of requesting an exemption review for the Alcohol and Tobacco questions. However, the CDCC instructed the project staff to include all of the Common Data Elements as created by the NIH until our request is reviewed and approved. Selected CDE questions are used in the basic demographic survey that will be asked once (See Basic Demographic Survey). Additional information about the CDE's and a copy of the CDE survey can be found on the RADx-UP website at: <https://radx-up.org/learning-resources/cdes/>

Due to the sensitive nature of select questions, the study team will provide this survey to the study participants at the end of the project to give the project team additional time to have the questions reviewed and approved to be exempted. The study staff will notify the participants during the consent they will have to complete this additional survey at the end of the project. The survey will be sent out via REDCap to the participant's email and explain to participants they are also given the option to not answer any questions they do not want to answer. The answers to the survey will be saved on REDCap and shared via a secure portal to the NIH's RADxUP data sharing hub.

Pre- survey – will be administered telephonically with study staff after the study participant is consented and enrolled in the study, at a time that is convenient for the study participant. The study staff, who are IRB approved, will send the survey to the participant to review prior to data collection, and will read the questions and answer choices aloud and input the participant's answer directly into REDCap under the Subject ID#. If participants state they are comfortable with completing the survey on their own, the study staff will send the survey via REDCap to the email. Participants enrolled in both control and case arm will complete this survey. Participants in the case arm will complete the survey before they attend the group classes and phone calls with the CHW.

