Aim 3 - After data cleaning, we will assess psychometric properties of all scaled measures, calculate descriptive statistics to ensure quality of the data (check distributions, examine outliers) and to describe study participants. Bivariate analyses will include independent t-tests models (or their nonparametric equivalents, e.g. Wilcoxon rank-sum test, differences between the groups in trust and self-efficacy. Paired-tests (or Wilcoxon signed-rank test) will be used to assess change within groups. Contingency table analyses will address intention to participate in COVID-19 testing and vaccination. We will then fit multiple regression models predicting change in COVID-19 testing- and vaccine-related knowledge, trust, and self-efficacy as a function of intervention group, racial/ethnic group, and possible interactions. We will use covariate adjustment approaches such as multiple linear and logistic regression models for the three outcomes (trust, self-efficacy, intent to participate) while controlling for demographic characteristics (e.g. age, gender, education, health status) and other potential covariates that will be identified a priori. We do not anticipate many missing data, given the format of completion. However, if we do have 10% or more missing, we will impute data using SAS PROC MI and SAS PROC MIANALYZE to implement these multiple imputation procedures. With respect to sample size, with 64 subjects in each of the two study groups, it will be possible to detect an effect size of 0.5 standard deviations in a quantitative outcome (a medium effect size in Cohen’s terminology) with 80% power and 2-sided 5% significance level.

VII. Funding

4. Check all types of funding sources for this study.

 Federal Grant/Contract  State, Local Government  International	 Private  Internal Grant Program  Departmental
--	--

 Industry	 Other:
2. Name of Funding Source (e.g. NIH)	NIH/National Library of Medicine
3. Grant/Contract Title*	A Community Health Worker Intervention to Identify and Decrease Barriers to COVID-19 Testing and Vaccination among Los Angeles County Department of Health Safety-Net Patients (Title of the Supplement to parent R01)

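### The change-score regressions for knowledge, trust and self-efficacy leave out the pre-survey score, giving up precision that data from both arms would supply

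*Protocol*

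**What the plan says.** Protocol VI.25 states both sides of the regression. The response is given as "We will then fit multiple regression models predicting change in COVID-19 testing- and vaccine-related knowledge, trust, and self-efficacy", and the predictors follow directly: "as a function of intervention group, racial/ethnic group, and possible interactions".

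The next sentence of VI.25 plans linear and logistic models for trust, self-efficacy and intent, "while controlling for demographic characteristics (e.g. age, gender, education, health status" being the named examples, together with "other potential covariates that will be identified a priori". Knowledge is not among those three outcomes, and the pre-survey score is not named.

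The score will be in hand. On the pre- and post-surveys, VI.9 says: "These surveys will be provided to both control and case arms, to measure three key measures: trust, self-efficacy". Intent is the third key measure, and knowledge is listed as a secondary one. VI.10 adds for the pre-survey: "Participants in the case arm will complete the survey before they attend the group classes and phone calls with the CHW".

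The sample-size statement in VI.25 claims 80% power at two-sided 5% for 0.5 SD in a quantitative outcome, "with 64 subjects in each of the two study groups". It does not say whether that SD belongs to the post score or to the change.

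**The concern.** An unadjusted change score subtracts the pre-survey score with its slope fixed at 1. Entering the score as a covariate lets the data estimate the slope. Unless the true slope happens to be 1, the fixed value leaves avoidable noise in the arm comparison. It also lets any chance baseline difference between the arms carry into the estimate for the sample at hand.

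The trial is sized at 80% with no reserve, so precision lost in the analysis is not covered elsewhere. If 0.5 SD means post-score SD, the change model as written has less than 80% power whenever r is below 0.5 (equal SDs). If it means change SD, the model keeps 80% but forgoes power that the same patients could give.

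**Working it through.** **Inputs.** From VI.25: 64 per arm, effect 0.5 SD, two-sided 5%, stated power 80%. Assumed, because the protocol gives neither: r = 0.3, 0.5 or 0.7, and the ratio s = pre SD / post SD. All figures ignore any clustering by class group or community health worker.

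**The plan's own figure.** For a two-sample t-test with 64 per arm and d = 0.5, the noncentrality is 0.5 × √(64/2) = 2.83 on 126 df. Power is 80.1%, and 64 is the smallest number per arm that reaches 80%. The stated figure reproduces.

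**Variances (post SD = 1).**
- Change model: 1 + s² − 2rs, which is 2(1 − r) when s = 1.
- With the pre-survey score added: 1 − r².
- Difference: (1 + s² − 2rs) − (1 − r²) = (s − r)². This is never negative, and is zero only when r = s.
- Ratio when s = 1: (1 − r²) / [2(1 − r)] = (1 + r)/2.

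**Power.** Noncentral t with d = 0.5/√variance, on 126 df for change and 125 df with the pre-score.

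| Equal SDs (s = 1) | r = 0.3 | r = 0.5 | r = 0.7 |
|---|---|---|---|
| Variance, change | 1.40 | 1.00 | 0.60 |
| Variance, with pre-score | 0.91 | 0.75 | 0.51 |
| Ratio (1 + r)/2 | 0.65 | 0.75 | 0.85 |
| Fall in standard error, 1 − √ratio | 19% | 13% | 8% |
| Equivalent change analysis, 64/ratio per arm | 98 | 85 | 75 |
| 0.5 in post-score SDs: change | 66.0% | 80.1% | 95.2% |
| 0.5 in post-score SDs: with pre-score | 83.7% | 90.0% | 97.6% |
| 0.5 in change SDs: change | 80.1% | 80.1% | 80.1% |
| 0.5 in change SDs: with pre-score | 93.6% | 90.0% | 86.1% |

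**Unequal SDs, post-score units.**

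| | r = 0.3 | r = 0.5 | r = 0.7 |
|---|---|---|---|
| Post SD 25% larger (s = 0.8), change | 74% | 86% | 97% |
| Post SD 20% smaller (s = 1.25), change | 55% | 69% | 88% |
| Either, with pre-score | 84% | 90% | 98% |

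**Chance imbalance (equal SDs).** The SD of the baseline difference between arms is √(2/64) = 0.177. An imbalance of that size shifts the change estimate by (1 − r) × 0.177, which is 0.12, 0.09 and 0.05 SD at the three values of r. The average shift over randomisations is zero.

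**Simulation.** 4,000 trials with 16 + 48 per arm and race/ethnicity in the model (equal SDs, post-score units) gave 66%, 81% and 95% for change, and 82%, 90% and 97% with the pre-score. Once the pre-score was included, the arm effects from change and post-score responses agreed to 1e-15.

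**The case against.** The strongest reply is that exact covariate lists usually belong in a statistical analysis plan, which is not shown here. The open clause on covariates chosen a priori could also admit the pre-survey score. This carries some weight for the adjusted models of trust, self-efficacy and intent, which is why they are not counted as defective. It does not settle the change regressions. The protocol gives both their response and their predictors, knowledge falls outside the open clause, and the score is not named anywhere.

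A second reply is that change analysis is a valid, standard estimator in a randomised trial. That stands: the point concerns efficiency and sensitivity to imbalance in the sample obtained.

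Third, VI.25 does not tie the 80% to the change regressions, and the lowest power figures need both a post-score reading of 0.5 SD and a low r. That also stands, and it is why both readings and a range are shown.

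Fourth, the gain is not guaranteed. When r equals s, for example both 0.8, the two variances are both 0.36 and adjustment costs one degree of freedom for nothing. That is an isolated case with a trivial cost.

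Finally, VI.8 places group notification before the pre-survey, so the statement of no average bias assumes that knowing the group does not alter the pre-survey answers. If it does, the change score is affected too, because it uses the same answers at full weight. The ordering is a separate matter and does not favour leaving the score out.

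**Conclusion.** The concern holds. As written, the regressions for change in knowledge, trust and self-efficacy omit a covariate that both arms supply and that improves precision in all but a knife-edge case. With equal SDs and r from 0.3 to 0.7, the standard error would fall by 19% to 8%. On the post-score reading the power gain is about 18 points at r = 0.3, 10 at r = 0.5 and 2 at r = 0.7. On the change reading it is about 13, 10 and 6 points. Unequal SDs widen the range, from about one point (r = 0.7, larger post SD) to almost 30 (r = 0.3, smaller post SD).

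These sizes rest on assumed correlations and SD ratios and on no clustering. The direction rests on algebra alone. The stated sample size is correct for its own assumptions, and intent is outside this point because it is not analysed as change.

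**What to change.** In VI.25, add the pre-survey score of the same scale as a covariate in the knowledge, trust and self-efficacy regressions, and keep race/ethnicity in the model as the stratification factor. The response can stay as change, because once the pre-score is included the arm effect is the same as with the post score as response. In the demographic-adjusted models, name the pre-survey value among the covariates fixed a priori, using pre-survey intent in the logistic model.

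The cost is about one sentence of analysis wording and one degree of freedom per model. It needs no new data, visits or participants.

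### Three unranked key outcomes, each with two or three between-arm analyses, share a sample size justified for one unnamed quantitative outcome at 5%

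*Protocol*

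**What the plan says.** All references are to section VI of the protocol.

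- **Outcomes.** Aim 3 (item 1) names trust, self-efficacy and intent to take part in testing and vaccination, without ranking them. Item 9 says the pre- and post-surveys are there "to measure three key measures: trust, self-efficacy" and intent, and sets a second tier apart from these: "Secondary measures included will use brief measures from the RADxUP and Phenx database of COVID protocols such as worry about COVID-19, knowledge" and others. So the three sit above the rest but are level with each other.
- **Analyses (item 25).** Trust and self-efficacy get a t-test or rank-sum comparison between arms. Regression models follow, "predicting change in COVID-19 testing- and vaccine-related knowledge, trust, and self-efficacy" from arm, race/ethnicity and possible interactions. Last come covariate-adjusted "multiple linear and logistic regression models for the three outcomes (trust, self-efficacy, intent to participate"). Intent gets contingency tables and then the adjusted model. Paired tests "will be used to assess change within groups".
- **Sample size (item 25).** The text says that "with 64 subjects in each of the two study groups, it will be possible to detect an effect size of 0.5 standard deviations". It locates that effect only "in a quantitative outcome", and the calculation is made "with 80% power and 2-sided 5% significance level". The outcome is not named. This is the only place where a significance level appears.

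Nothing in item 25 says which outcome or which model carries the conclusion.

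**The concern.** The power sentence describes one test of one outcome. The analysis paragraph describes eight between-arm tests of three outcomes: three each for trust and self-efficacy, and two for intent. With no lead outcome and no deciding model, a favourable p-value below 0.05 from any of them could be presented as the intervention working. The 5% and the 80% in the sample-size sentence would then describe neither the error rate nor the power of the claim being made. The sized outcome is also quantitative, so a statement in SD units does not cover intent, which is analysed categorically.

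**Working it through.** **Inputs from the protocol.** 64 per arm, effect 0.5 SD, two-sided 5%, 80% power (item 25). Three key outcomes (items 1 and 9). Between-arm analyses: 3 + 3 + 2 = 8 (item 25). 16 African American and 48 Latinx patients per arm (item 4).

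**Assumptions not in the protocol.** Correlation between outcomes 0 to 0.7; pre-post correlation 0.5 to 0.7.

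**1. The plan's own figure.** Two-sample t-test with 2 × 64 − 2 = 126 degrees of freedom and noncentrality 0.5 × √(64/2) = 2.83. Power is 80.1%, so the stated 80% is right for one quantitative outcome.

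**2. One analysis per outcome, each at 5%, no true effect.**

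- Either direction, independent outcomes: 1 − 0.95³ = 14.3%.
- Towards benefit, independent outcomes: 1 − 0.975³ = 7.3%, against 2.5% for one two-sided test.
- Correlated outcomes, by multivariate-normal simulation:

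| Outcome correlation | Either direction | Towards benefit |
|---|---|---|
| 0 | 14.3% | 7.3% |
| 0.3 | 13.6% | 6.8% |
| 0.5 | 12.5% | 6.3% |
| 0.7 | 10.9% | 5.5% |

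**3. All planned between-arm analyses open.** Null simulation at 64 per arm, 6,000 trials per setting. Trust and self-efficacy each get a t-test, a change regression and an adjusted regression. Intent gets a contingency test and an adjusted model, with the logistic model approximated by a linear one. Each cell gives the results at pre-post correlation 0.5 and 0.7.

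| Outcome correlation | Either direction | Towards benefit |
|---|---|---|
| 0 | 24.5%, 25.0% | 12.3%, 13.2% |
| 0.3 | 24.7%, 24.1% | 12.7%, 11.8% |
| 0.5 | 21.8%, 23.2% | 11.0%, 11.7% |
| 0.7 | 19.9%, 21.3% | 9.4%, 10.5% |

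Counting only the contingency test for intent (seven analyses, pre-post correlation 0.5, 4,000 trials) gives 22.6% at outcome correlation 0 and 18.7% at 0.7. Together the range is about 18-25% in either direction and 9-13% towards benefit. The within-arm tests are not counted in any of these figures.

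**4. Power if all three outcomes are kept.** Holm compares the smallest p-value with 0.05/3 = 0.0167. At that level, 64 per arm has 65.6% power for 0.5 SD by the same noncentral t calculation, and the effect detectable with 80% power is 0.58 SD. This is the first step; power for an outcome is higher once another has been rejected. Neither number applies to a categorical intent outcome.

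**The case against.** - **The sample-size sentence is correct, and 5% is only a planning level.** This stands. The protocol does not say that each outcome is tested at 5%, and it promises no trial-wide 5%. The error figures are therefore conditional on reading each result at the only level the protocol gives.
- **A multiplicity rule and the choice of deciding model are often left to the SAP, which is not at hand.** This stands for the absence of a rule as such. It does not answer the mismatch that is on the page: item 25 justifies the size for one unnamed quantitative outcome while the protocol carries three equal key measures, one of them categorical. If a SAP splits the error rate across the three, the 80% in item 25 no longer describes the result.
- **The analyses form an ordinary sequence from unadjusted to adjusted, and the two regression sentences may describe one modelling step.** That is a fair reading. Trust and self-efficacy would then have two analyses each, and the 18-25% would fall towards the 11-14% for one analysis per outcome. The question of which analysis decides would remain.
- **Aim 3 is a pre-test of a minimal-risk educational programme.** This lowers the urgency. It does not remove the ambiguity.

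Three stronger readings might be inferred and are not supported. First, the 11-25% is not the chance of a false claim of benefit, because it counts results in both directions. Second, knowledge does not displace intent: intent has its own contingency tables and is in the adjusted models, and a categorical outcome is naturally absent from a change-score regression. Third, the 80% would not carry over to whichever key measure is made primary, because it does not transfer to categorical intent.

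**Conclusion.** The point holds as an inconsistency between the outcome structure and the sample-size justification. Relative to the 2.5% chance of a false finding of benefit from one two-sided 5% test, the plan read at face value allows about two to three times that with one analysis per outcome (5.5-7%). With every planned between-arm analysis open it allows about four to five times (9-13%). The sizes rest on the assumed correlations and on reading each test at 5%. The direction does not: any second unadjusted look short of perfect correlation raises the figure. It is worth correcting before outcome data are seen, but it is not a bar to running a minimal-risk pre-test.

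**What to change.** Change item 25 in one of two ways.

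1. **One primary.** Name trust or self-efficacy as the primary outcome and specify one between-arm model that decides. The 80% power for 0.5 SD with 64 per arm then stands, tied to a named outcome.
2. **All three kept.** Apply Holm's rule across trust, self-efficacy and intent, with one between-arm model for each. Restate power for the two quantitative outcomes as about 66% for 0.5 SD at Holm's first step (0.58 SD detectable with 80% power), and add a separate power statement for intent as a categorical outcome.

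Under either option, label the remaining analyses as supportive, including the knowledge models and the within-arm changes.

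The cost is wording. Under the second option the stated power is less favourable. No extra patients or data are needed.

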
4. Study Population: Describe the characteristics of the participant population including, anticipated number, age range, gender, ethnic background and health status. Provide a candid discussion of potential problems related to the study population. Explain the rationale for the use of special classes such as fetuses, pregnant women, children, prisoners, or other vulnerable populations. If women, minorities or children are excluded, provide written justification.

a. Anticipated number of participants to be enrolled:
 
Aim 3: We will recruit a total of 142 patients to allow for approximately 10% attrition from each group. The final number of enrollees we require to successfully complete the study is 128 LACDHS patients composed of 32 African American and 96 Latinx patients who have not completed COVID-19 testing and/or vaccination, according to LACHDS records.
 
Each arm will have at least 64 LACDHS patients, comprised of at least 16 African American and 48 Latinx patients who have not completed COVID-19 testing and/or vaccination

b. Age range: 16 years old and older for Aim 3

c. Gender: all genders for Aim 3

d. Racial/ethnic background: African American and Latinx for Aim 3

e. Describe health status: LACDHS patients who did not complete a lab order for COVID-19 testing or COVID-19 vaccination from Aims 1 and 2

f. Foreign language translation and interpreter required? None

g. Other population characteristics: None

h. Potential problems related to study population: None

i. Vulnerable populations included in the study and the rationale: None

j. If excluding women, minorities, and children, please provide justification:
 
We will exclude children (those under the ages of 16) from this study.
 
Moreover, we are excluding patients under the age of 16 because a) they were not yet eligible for COVID-19 vaccination as of April 19, 2021 and b) decision making on COVID-19 testing and vaccination for children is usually made by their adult caregivers.

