We will utilize a randomized control design consisting of one treatment arm and a control arm. African American and Latinx patients who did not complete COVID-19 testing or vaccination will be recruited from the patient list obtained from Aim 1 data pull of the LACDHS EHR. The patient list obtained by the data pull will be filtered by the patient list provided by the LACDHS Vaccine Hesitancy Outreach Group. Based on the inclusion criteria, we will recruit a total of 142 patients to allow for approximately 10% attrition from each group. Patients who meet the inclusion criteria and agree to participate in the 2-month intervention will be randomly assigned to either the intervention or control arm.

We will stratify the randomization on the basis of race/ethnicity and we will use permuted blocks (**see table 3**). We will use a scheme such as found at randomization.com. Here we will define a block size of 4 subjects and determine a random permutation of 2 treatment and 2 control assignments employed the scheme in question. This is repeated to cover the request number of blocks in each stratum in order to randomize the total number of required subjects. We expect our study sample to reflect LACDHS patient population race/ethnicity stratification (9% African American and 68% Latinx).

Table 3 - Stratified Random Sampling

Block	Category	Number of participants to enroll
Block 1	African American + control	18
Block 2	African American + case	18
Block 3	Latinx + control	53
Block 4	Latinx + case	53

We will refer the control arm as “Group 1” and the intervention arm as “Group 2” for the purposes of explaining to prospective participants they will be randomly assigned to a group without compromising the integrity of the study.

Participants will need to complete the consenting process, complete a basic demographic survey, and wait to be randomly assigned to either Group 1 or 2. Once assigned to a group, the study staff will notify the participant of which group they were assigned to. The methodologies of

each respective group are detailed below after the participants are notified which group they were randomly assigned to.

Control Arm- Standard Treatment (Group 1):

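### Randomisation is stratified by race/ethnicity, but the simple between-arm tests are unstratified and no listed analysis of intent explicitly includes the stratum; the likely cost is small

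*Protocol*

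**What the plan says.** **Allocation.** Protocol section 8, Intervention Design: "We will stratify the randomization on the basis of race/ethnicity and we will use permuted blocks". The scheme is to "define a block size of 4 subjects and determine a random permutation of 2 treatment and 2 control assignments". Section 4 sets the intended composition: "Each arm will have at least 64 LACDHS patients, comprised of at least 16 African American and 48 Latinx patients".

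**Analysis.** Section 25 lists four kinds of between-arm analysis.

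- Trust and self-efficacy: independent t-tests or a nonparametric equivalent such as the rank-sum test. No stratum is mentioned.
- Intent: "Contingency table analyses will address intention to participate in COVID-19 testing and vaccination". No stratified form is mentioned.
- Change in knowledge, trust and self-efficacy: multiple regression on intervention group, racial/ethnic group and possible interactions. The stratum is included, but intent is not among these outcomes.
- Trust, self-efficacy and intent: linear and logistic models "while controlling for demographic characteristics (e.g. age, gender, education, health status) and other potential covariates that will be identified a priori".

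Section 9 names trust, self-efficacy and intent as the three key measures. Section 25 does not say which analysis is primary.

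**Power.** Section 25 takes 64 patients per arm, 80% power and a two-sided 5% level, and states that "it will be possible to detect an effect size of 0.5 standard deviations in a quantitative outcome".

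**The concern.** Stratified blocks force the arms to be nearly equal on race/ethnicity, so the difference in arm means varies less from trial to trial than under simple randomisation. A test that ignores the strata does not use this. It leaves the variance between strata in its error term and overstates the standard error whenever the stratum predicts the outcome. The p-value is then somewhat too large, and precision that the design has already secured is not collected.

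For trust and self-efficacy the change models recover this. For intent, nothing in section 25 explicitly does. The table is unstratified, the change models leave intent out, and the logistic model's covariates are given only by example. The same section therefore treats one of the three key measures differently from the other two, without a reason.

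**Working it through.** **Inputs from the protocol.** 64 per arm, effect 0.5 SD, two-sided 5%, 80% power (section 25). 16 African American and 48 Latinx patients per arm, so strata of 25% and 75% (section 4).

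**Assumed, because the protocol gives no figure.** The share of outcome variance explained by race/ethnicity (R²), taken from 0 to 0.20. For intent, a control rate of 40% in Latinx patients and an effect of 25 percentage points in both strata. Completers are taken to be exactly 16 and 48 in each arm.

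**1. The plan's own figure.** Signal = 0.5 × √(64/2) = 2.828. Normal-approximation power = Φ(2.828 − 1.960) = 80.7%. The exact noncentral-t value is 80.1%. The stated 80% reproduces, and it already describes an unadjusted two-group comparison.

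**2. Quantitative outcome, formula.** Set the total SD to 1, so that the effect is 0.5 of the outcome's SD. With arms balanced within strata, the difference in means has variance (1 − R²) × 2/64, but the unstratified test uses about 2/64.

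- True type I error of the unstratified test = 2 × [1 − Φ(1.96/√(1 − R²))]. R² = 0.05: 1.96/0.9747 = 2.011, giving 0.044. R² = 0.10: 1.96/0.9487 = 2.066, giving 0.039.
- Power, unstratified = Φ((2.828 − 1.960)/√(1 − R²)). R² = 0.05: 81.3%. R² = 0.10: 82.0%.
- Power, with stratum = Φ(2.828/√(1 − R²) − 1.960). R² = 0.05: 82.7%. R² = 0.10: 84.7%.

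**3. Quantitative outcome, simulation.** 60,000 runs per setting, t-test against a linear model with arm and stratum:

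| R² | Stratum gap (within-stratum SD) | Type I error, t-test | Power, t-test | Power, with stratum | Points forgone |
|---|---|---|---|---|---|
| 0 | 0 | 0.049 | 80.4% | 80.4% | 0 |
| 0.02 | 0.33 | 0.047 | 80.3% | 80.9% | 0.6 |
| 0.05 | 0.53 | 0.044 | 80.8% | 82.2% | 1.4 |
| 0.10 | 0.77 | 0.039 | 81.3% | 83.9% | 2.6 |
| 0.20 | 1.15 | 0.028 | 82.6% | 87.9% | 5.3 |

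In these settings the model with the stratum has a type I error of 0.049 to 0.050.

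**4. Intent, simulation.** 200,000 runs per setting, Pearson chi-square against Cochran-Mantel-Haenszel (CMH):

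| Gap between strata (points) | Null rejection, chi-square / CMH | Power, chi-square / CMH |
|---|---|---|
| 0 | 0.055 / 0.052 | 80.5% / 80.3% |
| 10 | 0.053 / 0.052 | 80.2% / 80.8% |
| 20 | 0.049 / 0.050 | 80.9% / 83.0% |
| 30 | 0.043 / 0.050 | 82.4% / 85.1% |

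The gain for intent is nil at no gap, about half a point at 10, and 2 to 3 points at 20 to 30. At this sample size the chi-square test is slightly above 5% when the strata hardly differ and clearly conservative only at a gap of 30.

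**The case against.** **The covariate list may already cover it.** The list is given by way of example, and section 9 counts race and ethnicity among the demographic survey's questions. The intended models may therefore include it, and a protocol commonly leaves closing such a list to the analysis plan. This stands: the text is silent, and silence is not exclusion. What remains is that section 25 names the stratum where it lists trust and self-efficacy, does not name it anywhere for intent, and specifies unstratified simple tests.

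**The simple tests are a first step.** They are called bivariate and regression models follow, so unadjusted results beside adjusted ones are routine. This also stands in part. But no analysis is named as primary, so nothing stops the simple table from carrying the conclusion on intent.

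**A reader might infer that the plan ignores the strata throughout.** It does not: the change models contain racial/ethnic group and its interactions for two of the three key outcomes.

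**A reader might infer that power falls below 80%.** Holding the within-stratum SD at 1 and adding a stratum gap of 1.0 SD gives Φ(2.828 − 1.96 × √1.1875) = 75.6%, and a gap of 0.5 SD gives 79.5%. But this shrinks the effect as a share of the total SD: 0.5/√1.1875 = 0.46 in the first case. Section 25 states the effect as 0.5 SD of the outcome. On the total-SD reading the unstratified test has about 83% and 81% power in those two cases, so the planned power is not lost.

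**A reader might infer that the protocol says race/ethnicity predicts these outcomes.** It compares African American and Latinx communities together with others, not with each other, and planning an interaction term asks the question without answering it.

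**Conclusion.** The point holds as a cheap improvement, not as an error that threatens the trial. The t-test, rank-sum test and contingency tables are unstratified although allocation is stratified, and intent is the one key outcome with no listed analysis that explicitly includes the stratum.

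The size is conditional. At an assumed R² of 0.05 to 0.10 the unstratified t-test is conservative (type I error about 0.044 to 0.039) and forgoes about 1.4 to 2.6 power points. The loss is nil if race/ethnicity is not prognostic and about 5 points at R² of 0.20. For intent it is at most about 3 points over the gaps examined. The stated 80% power is kept in every case. No bias in the estimated effect is involved, and where the stratum matters the error is on the conservative side.

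These sizes rest on the assumed R² range, the assumed intent rates and exact balance among completers.

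**What to change.** In section 25:

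- Name race/ethnicity, the stratification factor, as a fixed term in every adjusted model comparing the arms on trust, self-efficacy and intent. This matters most for the logistic model for intent.
- Use the Cochran-Mantel-Haenszel test, stratified by race/ethnicity, for the intent tables.
- If a rank test is used between arms for trust or self-efficacy, use the stratified (van Elteren) form.

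The cost is one or two sentences. The stratum must be known to randomise each patient, so no new data are needed and the sample size does not change.
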